8.6 Limitations of the Research Methods

Limitations include:

- Sampling bias of HCPs and patients (although measures are being put in place to minimise this).
- Participation bias (HCPs and patients or caregivers who volunteer to take part might be more likely to be interested in the product and RM), sampling will minimise bias owing to differential participation of different HCP types.

- Behaviour is being indirectly evaluated (as distinct from real-world behaviour).
- Survey is not relating use of tools to actual outcomes.
- It is not possible (for both ethical and practical reasons) to introduce a control (no exposure to RM tool) group, as RM tools must be universally offered in all countries as part of market authorisation.
- The level of education provided by different HCPs to patients / caregivers will affect how these answer survey questions it will not be possible to stratify patient / carer responses by HCP type (e.g. some child psychiatrists may provide excellent education whilst others do not). The survey will not link the patient / carer to their HCP.
- Social desirability bias (SDB), although potentially present in sample questionnaire
 studies, will be limited by avoiding direct interviewer questionnaires, by wording the
 introduction to emphasise that there are no "correct" answers, the measurement of
 behavioural choice rather than simply thinking, and also wording pre-ambles and
 question stems appropriately, to avoid any risk of inference as to "desirable" response.

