3.8 Study Size

Sample size is based upon an acceptable margin of error defined as less than 20% in the population of interest, with a significance level of < 0.05, and a correct response distribution to a knowledge-based question of 85%. This is anticipated to yield between 148 and 158 HCPs, and 148 to 158 patients participating, once the final evaluation has been completed.

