- 1. To determine the proportion of HCPs, patients and caregivers that are aware of the existence of the RM communication tools and how these tools were accessed (i.e. paper or electronic versions).
- 2. To determine who uses the RM communication tools, and how, when and how often they are used.
- 3. To determine the level of knowledge and comprehension of the key elements of identified risks of concern associated with ABILIFY® for the adolescent bipolar I mania indication (i.e. EPS, weight gain, somnolence and fatigue).
- 4. To assess the effect of the tools on the real-world risks that the educational tools have been designed to minimise, namely the maximum starting dose of ABILIFY® for the adolescent bipolar I mania indication is not exceeded, and the minimum age of patients receiving ABILIFY® for the adolescent bipolar I mania indication is not breached.
- 5. To evaluate the HCP, patient and caregiver behaviours via behavioural questions and scenarios.

The following tables illustrate which components of the surveys will be used to carry out these evaluations:

Table 1: Demographic questions

Annex	Questions examining participant demographics
Annex 1: HCP survey	1 to 4
Annex 2: Patient survey	1 to 3
Annex 3: Caregiver survey	1 to 3

Table 2: Understanding RM tool awareness and distribution

Annex	Questions designed to understand RM tool awareness
	and distribution
Annex 1: HCP survey	7, 8, 15, 16
Annex 2: Patient survey	4, 5
Annex 3: Caregiver survey	4, 5

ABILIFY®

Table 3: Understanding RM tool use and utility

Annex	Questions designed to understand tool use and	
	utility	
Annex 1: HCP survey	9 to 14, and 17 to 23	
Annex 2: Patient survey	6 to 11	
Annex 3: Caregiver survey	6 to 13	

For this survey, the intention is to primarily test knowledge indirectly, as meeting behavioural goals will require some degree of working-knowledge of ABILIFY[®] benefits and risk, when used for the adolescent bipolar I mania indication.

Tables 4 and 5 contain the questions that reflect understanding of how to take ABILIFY[®], how to treat ADRs (HCPs), and awareness of risks and what to do if risks are identified (patients / caregivers).

Table 4: Understanding knowledge of RM tool content

Annex	Questions designed to understand knowledge of tool	
	content	
Annex 1: HCP survey	24 – 35	
Annex 2: Patient survey	12 – 33	
Annex 3: Caregiver survey	14 – 35	

Table 5: Knowledge of potential or identified risks of concern

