HCPs will receive an honorarium (see below), which is payable only on survey completion, which compensates the HCPs for the time taken to participate in the survey and for providing PW with lists of patients / caregivers who will be randomised as part of the selection process. PW will be responsible for providing HCPs with access to the web-based survey by providing a web-link and a unique HCP identifier.

If survey drop-outs rates are high, or recruitment rates are low, recruitment will continue until the required numbers of surveys have been completed. The sampling method will also ensure that, for selected markets, specialist nurses and pharmacists who are involved in the care of patients on ABILIFY[®] (used for the adolescent bipolar I mania indication) are included as potential survey participants.

This approach is designed to both select HCPs and account for low response rates (e.g. a response rate of approximately 30%).

It should be noted that, in all countries involved in the study, ABILIFY® for the adolescent bipolar I mania indication will not be actively promoted. Hence, the pool of HCPs involved in treating these patients is expected to be small.

This approach should cover at least 20 to 30% of those who actively prescribe ABILIFY[®] for the adolescent bipolar I mania indication, which is anticipated to result in margins of error of < 20%, with confidence intervals in all countries of 95%, assuming 85% correct responses to knowledge based questions⁽⁵⁾.

The selection of the < 20% margin of error is driven by the small pool of HCPs treating patients within the adolescent bipolar I mania indication, and has been considered acceptable for similar evaluation of RM effectiveness surveys.

Bias will be avoided by random selection from a preliminary list, ensuring balance between the groups of Psychiatrists, Child / Adolescent Psychiatrists, Nurses and Pharmacists. To ensure that representatives from each target group are included in the study, the target lists will contain quotas of each subject type (e.g. 70 to 80% psychiatrists, 10 to 20% Nurses (if involved in treatment), and 5 to 10% pharmacists (if involved in treatment).

Random selection will then be carried out on each of the HCP types in order to generate lists containing appropriate proportions of each group. This approach will reduce the chances of significant selection bias (defined as particular HCP groups being favourably selected).

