8.3 Variables

Variables of interest and their definition include:

• Age of patient

Defined as the age of the patient at treatment initiation

Dose

Defined as the most recent dose taken before completing the survey

• Treatment duration

Defined as the length of time since the first dose taken for this indication, irrespective of whether treatment is continuous or interrupted

• HCPs' experience using ABILIFY® for the adolescent bipolar I mania indication
Defined as how many the HCP has treated with ABILIFY® for moderate to severe manic
episodes in bipolar I disorder in adolescents aged 13 years and older

• Usage of tools

Defined as whether the respondent has used the RM tools on one or more occasions

• Medical specialty

Defined as: psychiatrist, child / adolescent psychiatrist, nurse or prescriber

• Country

Country where the HCP or patient / caregiver resides

The key survey effectiveness evaluation metrics are shown in Table 7. Questions designed to measure: demographics, awareness and distribution, use and utility, knowledge of tool content, knowledge of identified or potential risks of concern and behaviours are described in Section 9.1.1.

ABILIFY®

Table 7: Key effectiveness evaluation metrics

_	Target Audience	
Metrics	НСР	Patient / Caregiver
Awareness of tools	X	X
Utilisation of tools	X	X
Knowledge and comprehension		
Symptoms requiring physician notification	X	X
Recommended age	X	N/A
Indicated dose	X	N/A
Indicated treatment duration	X	X
Risks of		
• EPS	X	X
 Weight gain 	X	X
 Somnolence 	X	X
• Fatigue	X	X
Ability to respond correctly to hypothetical	X	X
risk scenarios		
Behaviour		
Reviewing safety information with	X	
Patients / Caregivers		
Monitor for ARs and appropriate action if	X	
ADR is identified		
Distribution of Patient information	X	X
brochure to Patients / Caregivers		
Educating Patients / caregivers about	X	X
symptoms of EPS, weight gain,		
somnolence and fatigue and need to report		
them to a physician		

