8.4 Data Sources

The survey will include web-based structured questionnaires comprised of mostly multiple choice questions with some descriptive comments sections.

The surveys will determine:

- 1. General awareness of tools
- 2. When and how often the tools are used
- 3. If paper-based or web-based tools (downloads) are used

- 4. If HCPs use the tools themselves, if they give the PCIB to their patients / caregivers, and how and when they use the tools with Patients / Caregivers
- 5. If patients / caregivers received their PCIBs and if they use them
- 6. If the RM tools can be improved based upon feedback or proposals from HCPs, patients and caregivers
- 7. Knowledge and understanding of the specific ADRs associated with ABILIFY presented in the RM tools
- 8. If the tools promote appropriate behaviours (e.g. do physicians or other HCPs understand how to manage patients that may be experiencing ADRs and do Patients / Caregivers know what actions to take if they suspect they are suffering an ADR?)

For data protection, the identities of HCPs, Patients and Caregivers will be controlled by the use of unique identification codes provided to the participants by PW. The source ID numbers will be held securely on a separate system from that used to host the survey applications. This data will be used solely for the purpose of identifying whether the HCP, patient or caregiver has completed the survey.

Survey participants will be informed in the recruitment correspondence that the survey needs to be completed in a single sitting and that sufficient time (c.25 min for HCP s and c.15-20 min for the patients) needs to be set aside to complete the surveys. In the case of HCPs, the payment of the honoraria is contingent on completing the survey in this single sitting. This is to prevent users revising or studying for answers and using several sessions to answer a survey, thus reducing the possibility of biasing the survey by users answering the survey on multiple occasions.

The survey will be timed out after 20 minutes of continuous inactivity (e.g. user not interacting with the web-based survey for more than 20 minutes), which will also reduce the chances that participants consult reference sources. If users do not complete the surveys, their data will not be analysed and new participants will be sought.

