8.5 Study Size

The sample size will be driven by the estimated size of the population receiving ABILIFY[®] for the adolescent bipolar I mania indication. The sample size is based on an acceptable margin of error of less than 20% in the population of interest. This will yield between 148 to 158 HCPs and 148 to 158 patients / caregivers once the final evaluation has been completed.

The calculation to determine sample size was performed using a sample size calculator available from Raosoft⁽⁶⁾, and incorporated margins of error by country; hence, the range of 148 to 158 HCPs and 148 to 158 patients / caregivers. The calculation of sample sizes is described in Section 9.7.2.

To achieve a representative population of HCPs relevant to the local clinical practice of the country (e.g. nurses, ancillary HCPs and prescribers), and patients and caregivers, and to attain the ranges outlined above, approximately 20 to 30% of the actually prescribing / treating HCP

population would need to be invited as part of the recruiting process. For example, in the UK (estimated HCP population of 2188), a confidence level of 95% and 85% of correct responses to a knowledge based question, and a sample size of 13 HCPs, gives a margin of error of 19.36% (see Table 9).

It should be noted that ABILIFY[®] used in this indication is considered an area of specialised medicine. It is expected that some countries will have few prescribers, especially so since the product will not be actively promoted for use in the paediatric / adolescent population. The actual numbers surveyed will depend on the specific numbers of centres and HCP users. These values may be adjusted accordingly if there are particularly high or low national usages of ABILIFY[®] for the adolescent bipolar I mania indication at the time of the survey.

The following numbers of HCPs, and Patients or carers will be included per country:

UK	13 HCPs and 13 Patients / caregivers
Germany	13 HCPs and 13 Patients / caregivers
Spain	13 HCPs and 13 Patients / caregivers
Italy	13 HCPs and 13 Patients / caregivers
Sweden	13 HCPs and 13 Patients / caregivers
Denmark	13 HCPs and 13 Patients / caregivers
Norway	12 HCPs and 12 Patients / caregivers
Ireland	12 HCPs and 12 Patients / caregivers
Austria	12 HCPs and 12 Patients / caregivers
Portugal	12 HCPs and 12 Patients / caregivers
Cyprus/Greece	12 HCPs and 12 Patients / caregivers
Slovenia	12 HCPs and 12 Patients / caregivers

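### The survey introduction is to say there are no 'correct' answers, which is untrue for the knowledge items that the protocol evaluates by correct responses

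*Protocol*

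**What the plan says.** Section 8.6 lists social desirability bias as a limitation and names several countermeasures. One is wording the "introduction to emphasise that there are no 'correct' answers". The same bullet mentions pre-ambles and question stems separately, so the introduction reads as text for the survey as a whole. No type of item is exempted.

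Other sections rely on answers being right or wrong:

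- **Section 8.5:** the UK example assumes "85% of correct responses to a knowledge based question". Section 3.8 uses the same 85%, and section 8.2.2 derives its margins of error "assuming 85% correct responses to knowledge based questions".
- **Section 8.3, Table 7:** under knowledge and comprehension, one metric is "Ability to respond correctly to hypothetical" risk scenarios, for HCPs and for patients or caregivers.
- **Section 8.1:** primary endpoint 3 is "To determine the level of knowledge and comprehension of the key elements of identified risks of concern", namely EPS, weight gain, somnolence and fatigue. Section 7.2.1, objective 3a, adds knowledge of age range, dosage (HCPs only) and treatment duration.
- **Section 8.4:** the survey must be completed in one sitting, with the reason "This is to prevent users revising or studying for answers".

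Section 8.1 also states that "the intention is to primarily test knowledge indirectly", through items on behaviour.

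**The concern.** Respondents would be told that nothing is correct and would then take what is in part a knowledge test, under conditions meant to stop them looking things up. The reassurance suits questions on whether and how a brochure was used, or what the respondent thinks of it. On a question about which symptoms need a call to the physician, or about the indicated age range, it is false. Someone who believes it may choose the option they like instead of the one they know to be in the brochure.

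The absolute percentage correct carries much of the weight in this study. Section 8.6 rules out a control group, so an effect of the wording that is shared by all respondents cannot cancel in a comparison. Sections 3.2 and 6 say the results will set baseline levels, go to the EMA and possibly change the EU-RMP. The 95% confidence intervals promised in section 3.9 cover sampling error only.

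**Working it through.** **1. Do the protocol's own figures rest on a correct/incorrect outcome?** Inputs from section 8.5: p = 0.85, n = 13, N = 2188, 95% confidence. The margin for one proportion with finite population correction is

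1.96 × √[p(1−p)(N−n) / (n(N−1))] = 1.96 × √[0.1275 × 2175 / (13 × 2187)] = 0.1936.

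This reproduces the stated 19.36%. The planned precision is therefore that of a proportion of correct answers.

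**2. Where do the items fall?** From Tables 2 to 6:

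| Item type | HCP | Patient | Caregiver |
|---|---|---|---|
| Awareness and use (Tables 2, 3) | 7–23 | 4–11 | 4–13 |
| Knowledge of content (Table 4) | 24–35 | 12–33 | 14–35 |
| Behaviour (Table 6) | case studies | 23, 26, 29, 32 | 25, 28, 31, 34 |
| Age and dose (Table 5), outside the Table 4 range | 4, 5 | – | – |

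Every patient and caregiver behaviour item lies inside the Table 4 knowledge range. Removing those items leaves 22 − 4 = 18 pure knowledge items in each of these two surveys. For HCPs, Table 5 labels 24, 25, 28, 29 and 31–33 as case-study items and lists 26, 30, 34 and 35 without that label. The public text therefore does not fully separate case studies from other HCP knowledge items.

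**3. Illustration of size.** The inputs f and c are assumptions; nothing in the protocol supplies them. Let f be the share of knowers who answer by preference and c the chance that such an answer is still right. Observed % correct = 0.85(1−f) + 0.85·f·c.

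- f = 5%, c = 50%: 0.8075 + 0.0213 = 82.9%
- f = 10%, c = 25%: 0.7650 + 0.0213 = 78.6%
- f = 20%, c = 25%: 0.6800 + 0.0425 = 72.3%
- c = 0, the extreme case: 80.8% at f = 5% and 76.5% at f = 10%

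For f of 5% to 10% and c of 25% to 50%, the fall is 2.1 to 6.4 points. The whole-sample 95% half-width is 1.96 × √(0.1275/n), which is 5.8 points at n = 148 and 5.6 at n = 158.

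**4. Direction.** The formula in step 3 can only produce a fall, because it moves knowers only. Suppose instead that a share f of all respondents answers by preference with hit rate c. The observed value is 0.85(1−f) + f·c, which falls only if c < 0.85. If the appealing option is always the right one (c = 1), f = 10% gives 0.765 + 0.10 = 86.5%, a rise of 1.5 points. The sign depends on item content that is not public.

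**The case against.** The strongest reply is that this rests on one clause in a list of limitations. The questionnaires are annexes withheld until the study ends, so the actual introduction cannot be read. Pre-ambles and stems are also to be worded with care and may already carry suitable instructions for the knowledge items. This stands as far as harm is concerned: it cannot be shown that any respondent will be misled. It does not remove the conflict, because the stated commitment for the introduction has no restriction.

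Second, social desirability is a real threat here. Knowledge is tested mainly through behaviour, and people tend to report what they think they should do. This stands too, and it shapes the fix. Simply removing the reassurance from everything after the usage section would leave the Table 6 behaviour items and the HCP case studies without this safeguard, where it matters most.

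Third, correct/incorrect scoring is inferred. Table 7 marks which metric applies to which audience and gives no scoring rule, and the data analysis section is not in the public text. That is so, but an assumed 85% correct has no meaning unless answers are classified in that way.

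A reader might also take endpoint 3 to cover age, dose and duration. It names only the four adverse reactions. The other topics come from objective 3a, and starting dose and minimum age appear in endpoint 4. The argument is the same for either set of knowledge items.

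**Conclusion.** The protocol contradicts itself. A survey-wide statement that no answers are correct does not fit knowledge items that are evaluated by correct responses under objective 3 and endpoint 3. It is worth correcting because it touches a primary endpoint and there is no control group.

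A reader might infer that the percentage correct will be pulled down by an amount similar to the pooled confidence interval, or that the survey will record preference instead of knowledge. The documents support neither. The figures in step 3 depend on assumed values of f and c, the larger falls need most or all preference answers to be wrong, and step 4 shows that even the sign is open. Against the protocol's country-level tolerance of just under 20 points, an effect of this order would be hard to see. The supportable conclusion is that the statement is untrue for these items and could distort some answers, by an amount and in a direction that cannot be derived.

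**What to change.** Remove the blanket statement from the general introduction and word the instructions by item type:

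- **Awareness, usage and opinion items** (HCP 7–23, patient 4–11, caregiver 4–13): keep the statement that there are no correct answers.
- **Pure knowledge items** (patient 12–33 except 23, 26, 29, 32; caregiver 14–35 except 25, 28, 31, 34): use a neutral instruction such as 'please answer from what you know now, without looking anything up; results are reported in aggregate'.
- **Behaviour items in Table 6, HCP case studies, and HCP items 4–5 on age and dose**: use a preamble such as 'please indicate what you do or would do; results are reported only in aggregate'. This keeps a safeguard against social desirability without denying that correct answers exist.

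When the text is checked against the annexes, assign HCP items 26, 27, 30, 34 and 35 to the second or third group, according to whether they belong to a case study.

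The cost is a few sentences of survey text, to be settled before content is finalised (planned for Q1 2014 in section 5). The downside is slightly less reassurance before scored items, partly offset by the aggregate-reporting statement. Sample size and analysis do not change.

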8.7 Other Aspects

Not applicable.

9 PROTECTION OF HUMAN SUBJECTS

9.1 Ethics Committee Review and Informed Consent

9.1.1 Ethics Committee Review

This protocol will be submitted for review by ethics committees in each country wherein the study will be conducted, and the relevant national ethics committee will decide if any waiver applies.

9.1.2 Informed Consent

As part of the recruitment process, HCPs will be asked to encourage patients and carers to participate in the patient and carer surveys. HCPs will be given letters to give to the Patient / carer that contain an informed consent section. This section describes:

- 1. Why patients / carers are being invited,
- 2. What the survey aims to ascertain,
- 3. The duration of the survey,
- 4. How the data will be aggregated and anonymised, and
- 5. How personal data will be respected and protected (and how survey participants' identities will be protected through the use of unique identifiers).

Since the indicated patients are adolescents (aged between 13 and 17), parental / guardian consent will be required before patients are surveyed.

9.2 Confidentiality of Study Data

For the purposes of protecting a patient's identity, a unique code will be assigned to each patient, such as a series of numbers and/or letters (for example, OTXXXX-UK-00001). The survey data that is recorded with the patient's assigned code is called "key-coded data". Key-coded study data will be managed by the sponsor and / or its delegate/s (PW) in a study-specific electronic database. Data that could potentially directly identify the patient will not be collected in the SafetyGauge survey database. Only the PW Project Lead and PW Project Administrator have access to the link between the patient's assigned code and the patient's identity – which is held in a different application and a different physical location. Access to the survey data database in the SafetyGauge application is password-protected and may only be accessed by 2 nominated members of the PW IT staff. In case of an audit or inspection, however, subject to local laws and regulations, government officials, IRB / EC representatives, and sponsor representatives may be provided this information.

 $\mathsf{ABILIFY}^{ ext{@}}$

